An opportunity sample of 264 women will be recruited to the research. The sample size is powered to detect a minimal important clinical difference of 33% reduction in self-harm incidents over 8 weeks. This clinically significant difference is based on Hawton et al's systematic review of the efficacy of psychological and pharmacological interventions designed to reduce self-harm repetition [43]. From MOJ prison data, the average number of self-harm episodes over 8 weeks in the control group was 6.65 [3]. We modelled this with a Poisson distribution (mean and variance=6.65) and used Monte Carlo simulations with 1000 simulations to estimate the power for a range of sample sizes, with power defined as the proportion of estimated p-values less than 0.05 for null hypothesis testing (treatment effect is 0), against an alternative hypothesis (33% reduction in the log of the outcome). With 5% significance, to obtain 90% power, we will require 105 per group for the primary analyses. Based on WORSHIP II [6] we estimate 20% attrition so will recruit 132 per group at baseline. This level of attrition is not expected in the primary outcome, due to availability of prison data and the fact that self-reported incidents will be measured on a weekly basis, but allows for attrition in the secondary outcomes.

We expect that there will be several potential therapists because we are using trainees as well as qualified professionals. This means that each therapist will see a small number of participants each (mean≈6.6). In turn, we expect that the ICC will be small (though no estimates are available to inform our calculations), and since the number of participants per cluster is also small, the corresponding design effect indicates a small increase to the sample size would be required to take into account this clustering. We anticipate that this will be balanced by accounting for baseline prognostic factors in our statistical models, and that 90% power will be maintained with lower than 20% attrition rate for the primary outcome. We shall include a random effect for each therapist within the statistical analysis models.

Planned recruitment rate

The predicted figures have been calculated based on the number of women who will pass through each of the prisons, depending on their size and the recruitment rate achieved in WORSHIP II. The predicted figures (confirmed by HMPPS) are calculated as follows:

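### The protocol's 105 women per group does not follow from its stated inputs, which give about 25 (12 to 35 depending on how the effect is read), so the 90% power claim cannot be reproduced

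*Protocol*

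**What the plan says.** All of the inputs are in one paragraph of the Protocol, under Sample size calculation.

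- Target: "The sample size is powered to detect a minimal important clinical difference of 33% reduction in self-harm incidents over 8 weeks".
- Control rate: "the average number of self-harm episodes over 8 weeks in the control group was 6.65".
- Model: "We modelled this with a Poisson distribution (mean and variance=6.65) and used Monte Carlo simulations with 1000 simulations".
- Test: "power defined as the proportion of estimated p-values less than 0.05 for null hypothesis testing (treatment effect is 0". Sidedness is not given.
- Alternative: "against an alternative hypothesis (33% reduction in the log of the outcome".
- Result: "With 5% significance, to obtain 90% power, we will require 105 per group for the primary analyses".
- Attrition: "we estimate 20% attrition so will recruit 132 per group at baseline", although "This level of attrition is not expected in the primary outcome".

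The next paragraph expects about 6.6 participants per therapist and a small intracluster correlation with no value available. It adds nothing to the 105 for clustering and relies on baseline covariates to offset it. The Protocol's own statistical analysis plan section names a mixed Poisson model with baseline covariates and a therapist random effect. No dispersion parameter for differences between women is given anywhere.

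**The concern.** The paragraph gives a distribution, mean, variance, effect, significance level and power, so the sample size should follow from it. For a Poisson count with a mean near 6.65, 105 per group looks several times too large for a reduction of a third.

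The effect is also described twice, and the descriptions differ. A 33% fall in incidents takes the mean from 6.65 to 4.46. A 33% fall in the log takes it to 3.56 if read literally, or to 4.78 if it means a log coefficient of -0.33. A reader cannot tell which effect was simulated.

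What is at stake is the 90% power figure, on which the trial's size rests. If the reported inputs are not those that were run, nobody can say which effect, or how much variation between women, the trial was sized for.

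**Working it through.** **Inputs.** Control mean m = 6.65, Poisson, 5% significance (taken as two-sided), 90% power and equal groups, all from Sample size calculation.

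**The step that reproduces.** 105 / (1 - 0.20) = 131.25, rounded up to 132 per group, 264 in total. Attrition is therefore applied after the 105 and does not explain it.

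**The step that does not.** For a Wald test on the log rate ratio (RR):

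n per group = (1.960 + 1.2816)² × (1/m + 1/(m·RR)) / ln(RR)², where (1.960 + 1.2816)² = 10.507.

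| Reading of the effect | RR | Treated mean | Calculation | n per group |
|---|---|---|---|---|
| 33% fewer incidents | 0.670 | 4.456 | 10.507 × (0.1504 + 0.2244) / 0.1604 | 24.6 (25) |
| Log coefficient -0.33 | 0.719 | 4.781 | 10.507 × (0.1504 + 0.2092) / 0.1089 | 34.7 (35) |
| Log mean cut by 33% | 0.535 | 3.559 | 10.507 × (0.1504 + 0.2810) / 0.3909 | 11.6 (12) |

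Simulating Poisson counts at RR 0.67 (5,000 runs) gives 91% power at 25 per group and 100% at 105. By the formula, 105 per group exceeds 99.9% power under all three readings.

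**Other routes tried at RR 0.67.** One-sided testing gives 20.0 (21), a difference in means 25 to 30, a square-root transform 24, and 99.9% power 60. None reaches 105. Simulation error is no explanation: with 1,000 runs at 90% power the standard error is √(0.9 × 0.1 / 1000) = 0.0095, about one percentage point.

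**What would give 105.** Changing one input at a time:

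- a reduction of about 17% (RR 0.834);
- a control mean of about 1.56;
- a design effect of 105 / 24.6 = 4.3, which at 6.6 per therapist needs an intracluster correlation of (4.28 - 1) / 5.6 = 0.58;
- a negative binomial with variance m + k·m². This adds 2k to the variance term, so k = (105 × 0.1604 / 10.507 - 0.3748) / 2 = 0.61. The control variance is then 6.65 + 0.614 × 6.65² = 33.8, about five times the mean.

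The protocol states none of these. The last contradicts its own variance of 6.65, and the design effect contradicts its expectation of a small intracluster correlation.

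**Power if counts are overdispersed.** For RR 0.67 with an overdispersion-valid standard error and no covariate adjustment, power = Φ(0.4005 / √((0.3748 + 2k)/n) - 1.96). The values of k are assumed.

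| k | 105 per group | 132 per group |
|---|---|---|
| 0.5 | 93.8% | 97.5% |
| 1 | 75.9% | 84.7% |
| 1.5 | 60.8% | 70.7% |
| 2 | 50.1% | 59.5% |

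Power is 90% at k = 0.61 with 105 per group. With 132 it is 90% at k = (132 × 0.1604 / 10.507 - 0.3748) / 2 = 0.82.

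**The case against.** The best defence is that the number may be sounder than its explanation. Under the stated inputs, 264 women are more than enough. The 105 may also contain a sensible allowance for extra variance that was not written down. Three features of the plan help further. Attrition in the primary outcome is expected to be below 20%, so the analysed number should lie between 105 and 132 per group. Baseline covariates will absorb some of the variation between women: as an illustration, if they removed 20 to 40% of k = 1, power would be 83 to 90% at 105 and 91 to 96% at 132. And k = 0.61 is only one of several back-solved explanations.

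All of this stands, and it limits the point. A reader might infer that the 90% claim fails under ordinary overdispersion. The documents do not support that: they give no dispersion, so calling any value ordinary would be an outside judgement, and k = 0.5 still leaves 94% at 105. A reader might also infer that a null result could not rule out the 33% effect. That would depend on the confidence interval obtained, not on planned power.

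The table also presumes a valid standard error. If a Poisson model ignored overdispersion between women, the main hazard would be false positives: simulated type I error without clustering was about 35% at k = 0.5 and 49% at k = 1, at 105 per group. That is a matter for the analysis model, separate from this point.

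None of this recovers 105 from the stated inputs or reconciles the two wordings of the effect.

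**Conclusion.** The point holds as a failure of derivation. The stated inputs give about 25 per group for a 33% reduction in incidents, and 12 or 35 under the two log readings. The stated figure is roughly four times the first of these. Either an input is misreported or a variance allowance is missing from the text, and the documents do not show which. The 90% figure therefore has no reproducible basis, and the effect that was powered is not uniquely defined.

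Whether actual power is above or below 90% cannot be settled from the protocol. For rate ratio 0.67 it falls below 90% if k exceeds about 0.61 at 105 per group or about 0.82 at 132. These limits assume a two-sided test, a negative binomial, a standard error that allows for overdispersion, no covariate adjustment and no therapist clustering.

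**What to change.** In the sample size paragraph:

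1. State the inputs actually simulated: distribution, dispersion, control mean, effect and sidedness.
2. Give one effect definition on the rate-ratio scale. Choose between the two present wordings by checking what was run; do not delete either without that check.
3. Re-run the simulation with a stated dispersion, and replace the flat 90% with power at 105 and 132 per group over a range such as k = 0.5 to 2.
4. Optionally, check k on the pilot counts pooled across arms. The 43 planned pilot women give only a rough estimate: with a true k of 1, simulated estimates ranged from about 0.58 to 1.63 (95% range), which corresponds to 96% down to 67% power at 132.

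The cost is one rewritten paragraph and a short simulation. No extra recruitment is needed for this correction. The drawback is that the stated power may become less favourable.

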Where a participant is able to consent but later becomes incapacitated, the participant will be suspended from the study. If their capacity returns they will be given the opportunity to re-enter the study. When a participant is formally withdrawn from the study, by their own choice or due to ongoing incapacity, identifiable data already collected with consent will be retained and used in the study, if they consented to retention at baseline. No further data will be collected, or any other research procedures carried out, on or in relation to the participant.

Randomisation

WORSHIP III	IRAS No: 241606

Kings Clinical Trials Unit will build a randomisation system. Randomisation will be at the individual level by block randomisation with randomly varying block sizes, stratified by prison. The trial manager/RAs will access the randomisation system, randomise the participants and receive randomisation alerts and will inform the other researchers and the therapists of the allocation for each participant.

Blinding

Blinding of trial participants and care providers is not possible due to obvious differences between the interventions. It is not practical for the research assistants/research associate to be blind as they will need to coordinate the delivery of the therapy in their study prisons. The outcome assessors who collect the post intervention data (8-weeks) and follow-up data (12-weeks) will be blind to the intervention groups. Outcome assessors will include trained Research Nurses/CSOs/volunteers/peer mentors/ students. These outcome assessors will be security trained so they can enter the prison independently to complete their assessments and will have no other involvement in the research. The trial manager will ensure that outcome assessment takes place at a time and in a location of the prison which will avoid the assessors interacting with the RAs and therapists in a way that could reveal any participant's allocation. If a participant is transferred to a remote site which cannot be accessed by the outcome assessors, they will be followed up by a research assistant who is unaware of their randomisation status. E.g. the RA from London will follow up the RA from Manchester's participants.

Emergency Unblinding

Emergency unblinding should not be necessary as the investigators and therapists will not be blinded and will be able to respond to any serious adverse events in accordance with the protocol.

Baseline data

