Analyses of the quantitative data will use an intention-to-treat (ITT) approach with analysis of randomised participants, regardless of non-compliance with protocol. Analyses will post-date final follow-up assessments, with consideration of potential biases from loss to follow-up. The primary outcome (number of incidents of self-harm at 8 weeks) will be analysed using a mixed Poisson model that adjusts for pre-specified baseline covariates and includes a random effect for therapist (since there are multiple therapists per site).

Secondary outcomes will be analysed using a linear mixed model over all repeated measures. Time will be included as a categorical factor, as well as a time*treatment interaction. We will estimate the effect at 8 and 12 weeks separately and report these as an adjusted mean difference.

WORSHIP III	IRAS No: 241606

We can explore possible subgroup effects (particularly around ethnicity, see above) using a treatment by covariate interaction in the fixed part of the model. We are not powered to detect significant interactions and are not currently pre-specifying any potential subgroups.

As secondary analyses, we shall explore a dose-response relationship using randomisation as an instrumental variable for number of sessions received. If there are significant effects on secondary outcomes which are also potential mechanisms (e.g. hopelessness, self-esteem), we shall perform a mediation analysis to test if these account for any observed treatment effects on the primary outcome using causal mediation approaches.

The sensitivities of all treatment effect estimates to missing outcome data will be explored; these models will explore the robustness of the treatment estimates to whatever small amount of missing data there is. The main analysis will use all available data that we believe are valid under the assumption of missing at random. We shall then use a suite of sensitivity analysis to explore the robustness of the primary analysis to departures from assumptions, including all randomised participants. If required, sensitivity analyses will include multiple imputation, and imputing a range of values for missing data under missing not at random assumptions.

Qualitative Analysis

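### The primary Poisson model has a therapist effect but no term for variation between women, and does not say how TAU women enter that effect

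*Protocol*

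**What the plan says.** Under *Statistical analysis plan*, the protocol states that the 8-week incident count "will be analysed using a mixed Poisson model that adjusts for pre-specified baseline covariates and includes a random effect for therapist". *Sample size calculation* repeats the therapist term: "We shall include a random effect for each therapist within the statistical analysis models". Neither section mentions a dispersion parameter, a woman-level random effect, a negative binomial alternative or a robust standard error. The covariates are not named.

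The trial is "powered to detect a minimal important clinical difference of 33% reduction in self-harm incidents over 8 weeks". For the control mean, the protocol says that "the average number of self-harm episodes over 8 weeks in the control group was 6.65". For the spread it says "We modelled this with a Poisson distribution (mean and variance=6.65". The result is: "With 5% significance, to obtain 90% power, we will require 105 per group for the primary analyses".

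*Trial procedures* and *Trial treatments* give a trial therapist to the PIT arm only. TAU women continue with whatever their prison provides. Nothing says which level of the therapist effect a TAU woman belongs to.

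**The concern.** A Poisson model with only a therapist effect forces the variance to equal the mean among women who share a therapist. If TAU women sit outside the therapist effect, it forces this across the whole TAU arm. Eligibility requires self-harm in the last month and a current or recent ACCT. That admits a woman with one act and a woman who self-harms repeatedly, so equal underlying rates are implausible.

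There are two consequences. First, standard errors that ignore variation between women are too small. Second, the therapist effect is the only place in the model where that variation can go. It is then partly absorbed into the therapist variance, and what this does to the treatment contrast depends on how the TAU women are coded. With a log link, an arm that carries a random effect has an intercept conditional on that effect. An arm without one has a marginal mean. The two are not comparable without a correction.

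At stake are the primary p-value, confidence interval and rate ratio of a trial meant to inform roll-out across women's prisons.

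**Working it through.** **1. The plan's own figure.** Inputs from *Sample size calculation*: control mean 6.65, rate ratio 0.67 (treated mean 6.65 × 0.67 = 4.46), 5% significance (taken as two-sided) and 90% power.

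For Poisson counts, n per group = (1.960 + 1.282)² × (1/6.65 + 1/4.46) / ln(0.67)² = 10.51 × 0.375 / 0.160 ≈ 25.

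Monte Carlo power under Poisson was 0.91 at 25 per group and about 1.00 at 105. The simulation's alternative is worded differently ("against an alternative hypothesis (33% reduction in the log of the outcome"). Read literally, the treated mean is 6.65^0.67 = 3.56 and n is 12. Neither reading gives 105. The attrition step does reproduce: 105 / 0.8 = 131.25, rounded up to 132.

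With negative binomial counts (variance = m + k·m²), n = 10.51 × (0.375 + 2k) / 0.160. Setting n = 105 gives k ≈ 0.61, so variance/mean = 1 + 0.61 × 6.65 ≈ 5.1. The same formula gives 64, 156 and 287 per group at k = 0.3, 1 and 2.

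**2. Behaviour under a true null.** Simulation inputs: 105 per arm, mean 6.65, true rate ratio 1, 20 therapists (132 / 6.6), gamma-mixed Poisson counts, no real therapist differences and no covariates. The mixed Poisson model was fitted by maximum likelihood with adaptive quadrature, 1000 runs per row. Each of the three coding columns gives the rejection rate at nominal 5% and the mean rate ratio (RR).

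| k (assumed) | Var/mean | Therapist effect in PIT only | Each TAU woman her own cluster | TAU as one cluster | Poisson, sandwich SE |
|---|---|---|---|---|---|
| 0.3 | 3.0 | 16.1%, RR 0.97 | 4.0%, RR 1.07 | 1.9%, RR 0.97 | 7.1% |
| 0.61 | 5.1 | 17.7%, RR 0.94 | 7.0%, RR 1.19 | 0.1%, RR 0.95 | 5.9% |
| 2 | 14.3 | 31.5%, RR 0.83 | 44.6%, RR 1.88 | 0.0%, RR 0.84 | 5.4% |

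In the PIT-only column, most rejections favour PIT: 11.8% against 4.3% favouring TAU, 15.1% against 2.6%, and 29.6% against 1.9%. A second implementation of that coding gave 14%, 20%, 23% and 41% at k = 0.3, 0.61, 1 and 2, with RR 0.97, 0.94, 0.90 and 0.82.

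With k = 0 the PIT-only model rejected in about 5% with RR 1.00 (150 runs), so overdispersion is the cause. A negative binomial regression rejected in 5.3% at k = 0.61 and 4.3% at k = 2 (300 runs each). The sandwich and negative binomial analyses both had mean RR 0.99–1.00.

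**3. Why the PIT-only ratio shifts.** The mean fitted therapist variance s² was 0.053, 0.111 and 0.413, although no therapist differences were simulated. The PIT intercept then understates the PIT mean by about exp(−s²/2) = 0.97, 0.95 and 0.81, close to the simulated ratios.

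**4. A lower mean.** At mean 1.02 and k = 2, the PIT-only coding rejected in 16% with RR 0.86 (150 runs).

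**The case against.** The strongest reply is that the protocol leaves room. It does not say the therapist effect is confined to PIT, coding of the unclustered arm is ordinary SAP detail, and an SAP not shown here could add a dispersion term. This stands as far as direction goes. A reader might infer that the model is bound to bias the result towards PIT. The documents do not support that: with each TAU woman as her own cluster the bias runs towards TAU, and with TAU as one cluster the test hardly ever rejects. It does not rescue the named model, since none of the three codings gives both a correct error rate and an unbiased ratio once k is appreciable. The Poisson form is a stated choice, made in both the analysis and the sample size.

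The second reply is that the plan adjusts for baseline covariates and the simulations above do not. This also stands in part. Suppose one covariate explains 50–70% of the between-woman variance in log rate (an assumption; lognormal heterogeneity, 300 datasets per cell). PIT-only rejection then falls from 16%, 24% and 32% to 11–13%, 16–19% and 16–22% at k = 0.5, 1 and 2. The null ratio moves from 0.96, 0.93 and 0.86 to 0.98–0.99, 0.96–0.97 and 0.92–0.97. The bias becomes small in most cells, but the excess false positives remain.

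Third, k is not in the documents. That is true, and every magnitude depends on it. At k = 2, separate runs of the PIT-only model without covariates ranged from 28% to 41%, more than simulation error explains, so only the broad range should be used.

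A reader might also infer that the stratification factor has been left out, given "Randomisation will be at the individual level by block randomisation with randomly varying block sizes, stratified by prison". Prison may be among the unnamed pre-specified covariates, so no error is shown.

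**Conclusion.** The concern holds in conditional form. The protocol fixes a primary model with no allowance for variation between women, and its variance assumption conflicts with its own sample size by a factor of about four (105 against 25). It also leaves undefined how half the sample enters the only random effect. With overdispersion, the p-value and confidence interval cannot be trusted under any of the three codings examined. If the effect is PIT-only and there are no covariates, false positives are roughly 14–20% at k = 0.3–0.61 and about 30–40% at k = 2, with a null rate ratio of about 0.97 to 0.82.

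This rests on an assumed k, gamma-mixed counts, 20 therapists and a mean of 6.65. Useful covariates would lower the figures. The match between 105 and k ≈ 0.61 does not show that the sponsor used that value. It shows only that the stated n and the stated variance cannot both describe one calculation.

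**What to change.** Replace the primary model with a negative binomial (or Poisson) regression that reports the marginal rate ratio. Use cluster-robust standard errors with therapist as the cluster in PIT and each TAU woman as her own cluster, and a small-sample correction because there are only about 20 therapists. The clustering matters: with an assumed therapist variance of 0.1 on the log scale and no other overdispersion, the sandwich without therapist clustering rejected a true null in 14.7% of 150 runs.

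If a mixed model is preferred, make it negative binomial, state that the therapist effect applies in PIT only, and report the marginal rate ratio, not the conditional one.

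Prior self-harm frequency is already collected on the Self-Harm History Questionnaire and can be among the covariates. In the sample size section, state the dispersion that 105 per group assumes.

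The cost is protocol and SAP wording and a few lines of code, with no new data. The downside is wider confidence intervals. Ignoring therapist clustering and covariates, power at 105 per group is 90% at k = 0.61, 76% at k = 1 and 50% at k = 2.
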